7.7 Replacement of individual subjects when deferred consent could not be obtained

When deferred consent is not obtained after randomization and provisional inclusion of a patient, the randomized subject will be replaced. In the randomization log these cases will be recorded without patient-specific data. The randomization subjects will be replaced in order to retain properly distributed randomization groups.

In the sample size calculation, a dropout rate of 10 % has been taken into account.

8. SAFETY REPORTING

8.1 Temporary halt for reasons of subject safety

In accordance to section 10, subsection 4, of the WMO, the sponsor will suspend the trial if there is sufficient ground that continuation of the trial will jeopardise subject health or safety. The sponsor will notify the accredited METC without undue delay of a temporary halt including the reason for such an action. The trial will be suspended pending a further positive decision by the accredited METC. The investigator will take care that all subjects are kept informed.

8.2 Secondary endpoints for safety

Since we compare two ventilation strategies that are currently used in standard care, additional risks are not expected. Furthermore, the study population consists of critically ill patients, with a high incidence of death or life-threatening events due to the severity of their illness (the hospital mortality in ventilated ICU patients is 21% ³⁴). Therefore, we propose to report the secondary endpoints of this trial, which incorporate ventilation specific complications, in a line listing two times per year to the METC to monitor safety of both treatment strategies. The METC will receive a line listing of the secondary endpoints incorporating ventilation specific ventilation complications (see below). These endpoints will be specified per study arm in the line listing without disclosing the specific arms.

Those ventilation specific complications include:

- ICU mortality
- Incidence of development of ARDS
- Incidence of severe hypoxemia
- Incidence of rescue therapy for severe hypoxemia and/or severe atelectasis:
 - Recruitment strategies
 - Prone positioning
 - Bronchoscopy for opening atelectasis

8.3 Data Safety Monitoring Board (DSMB)

An DSMB will be installed to monitor safety and the overall conduct of the trial. The DSMB will compose of 4 individuals who will be invited, one of which will be the chairman.

- The DSMB will first meet after inclusion of the first 150 patients, approximately 6 months after the first patient is enrolled.

- Subsequent to this meeting the DSMB will meet virtually every 6 months
- The DSMB will review the overall status of the program, number of patients enrolled overall and in each center, adherence to the protocol overall and by each center.
- The DSMB will monitor safety of both ventilation strategies by monitoring the secondary endpoints of ventilation specific complications.
- The following DSMB individuals will be invited:
 - [name], MD PhD, St James's University Hospital, Dublin, Ireland
 - [name], MD, Universita degli Studi dell'Insubria, Varese, Italy
 - [name], MD PhD, Canberra Hospital, Garran, Australia
 - Prof. [name], MD PhD, Hospital de Sabadell, Sabadell, Spain

The report and/or advice of the DSMB will only be sent to the sponsor of the study, the Academic Medical Center. Should the sponsor decide not to fully implement the advice of the DSMB, the sponsor will send the advice to the reviewing METC, including a note to substantiate why (part of) the advice of the DSMB will not be followed.

9. STATISTICAL ANALYSIS

9.1 General considerations

The statistical analysis will be based on the intention-to-treat principle. In addition, we will perform a per-protocol analysis to check for robustness of results. The intention-to-treat analysis includes all patients as randomized regardless of whether they received the randomized treatment or other protocol deviations. Per-protocol group analysis only considers those patients who completed the treatment according to the originally allocated protocol. In this non-inferiority trial we include a superiority, primary effect analysis. If the non-inferiority criterion is satisfied, a secondary analysis of the primary endpoint for superiority will be conducted. When appropriate, statistical uncertainty will be expressed by the 95% confidence levels. P-values of 0.05 are used for statistical significance. All statistical analysis will be performed with the R version 3.3.2.

9.2 Primary study parameter

The primary outcome is the number of ventilator-free days and alive at day 28 after ICU admission. The null hypothesis entails that ventilation with the 'restricted PEEP'-arm is inferior by a margin of 10% to ventilation with the 'liberal PEEP'-arm. If the 95% CI upper bound for inferiority of the 'restricted PEEP'-arm is < 10%, the null hypothesis of inferiority is rejected. If the non-inferiority criterion is satisfied, then a secondary analysis of the primary endpoint for superiority will be tested. We will use an appropriate nonparametric analysis method to evaluate the confidence interval for the difference between the two medians of the ventilator-free days from both PEEP arms. Additionally, time to freedom from mechanical ventilation is expressed with Kaplan-Meier curves. Differences between both PEEP arms will be analyzed using the log-rank test.

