4.4 Sample size

Group size calculation is focused on demonstrating non–inferiority. When the sample size in each is 445, an one–sided non–inferiority t–test (targeted at 0.05 significance level) for the difference in means of log–transformed normalized data has a 80% power to reject the null hypothesis that the number of VFD–28 in the 'restricted PEEP'–arm is inferior to the number of VFD–28 in the 'liberal PEEP'–arm by a margin of 10% anticipating on a coefficient of a variation of 0.70 (www.stichting-nice.nl), in favor of the alternative hypothesis that the number of VFD–28 in the 'restricted PEEP'–arm is non–inferior.

The choice for a margin of 10% is motivated by what we consider acceptable from a clinical point of view as the maximal acceptable reduction of the ventilator–free period for non–inferiority. Clinically this margin means that an increase of > 10% in the

duration of mechanical ventilation will reduce the VFD-28 with > 12 hours (calculated over the expected mean duration of mechanical ventilation of 5 days) (<http://www.stichting-nice.nl>) which will be considered inferior. To allow for an anticipated drop out of 10% a total of 980 patients will be included.

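### Does the unstated side of the 95% upper bound in Section 9.2 put the non-inferiority rule at odds with the one-sided 0.05 test in Section 4.4?

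*Protocol*

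**What the plan says.** Three places in the protocol bear on the level of the primary test.

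- **Section 4.4 (Sample size)** rests on "an one–sided non–inferiority t–test (targeted at 0.05 significance level"), applied to ventilator-free days at day 28. The calculation is "for the difference in means of log–transformed normalized data", and the design "has a 80% power to reject the null hypothesis" of inferiority "by a margin of 10% anticipating on a coefficient of a variation of 0.70". This gives 445 per arm, raised to 980 in total for 10% dropout.
- **Section 9.2 (Primary study parameter)** restates the same null hypothesis and the same 10% margin. It rejects inferiority by a rule that begins "If the 95% CI upper bound for inferiority of the" restricted-PEEP arm and requires that bound to lie below 10%. The side of the interval is not given. The interval method is left open: "We will use an appropriate nonparametric analysis method" for the difference between medians.
- **Section 9.1 (General considerations)** says, for all analyses, "When appropriate, statistical uncertainty will be expressed by the 95% confidence levels" and "P-values of 0.05 are used for statistical significance". Neither statement gives a side.

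The protocol nowhere mentions a 90% interval, and nowhere says that Section 9.2 departs from the level in Section 4.4.

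**The concern.** A 95% confidence interval with no qualifier is usually taken to be two-sided. Its upper limit leaves 2.5% in the tail, so using that limit as the non-inferiority criterion is a one-sided 0.025 test. Section 4.4 used one-sided 0.05. On that reading the trial would be judged by a stricter rule than the one it was sized for, and the stated 80% power would not hold.

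Two features make the two-sided reading plausible. Section 9.1 uses 95% as the general level for expressing uncertainty. Section 9.2 also follows non-inferiority with a superiority test, and one two-sided 95% interval is a common way to serve both.

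What would be at stake is power, and some discretion over a borderline result in an open-label trial: a modest observed shortfall could pass on one reading and fail on the other. An inflated false-positive rate is not at stake.

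**Working it through.** **Inputs, all from Section 4.4:** ratio margin 0.90 (10%), coefficient of variation 0.70, one-sided level 0.05, power 80%, 445 per arm, 980 in total. One assumption is added because the section does not state it: the true ratio is 1. It reproduces the protocol's figure.

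**Log-scale quantities**

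- SD = sqrt(ln(1 + 0.70²)) = sqrt(ln 1.49) = 0.6315
- Margin = −ln(0.90) = 0.1054

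**Step 1: reproduce 445.** The formula is n per arm = 2 (z₁₋α + z₀.₈₀)² SD² / margin².

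- One-sided 0.05: 2 × (1.645 + 0.842)² × 0.3988 / 0.01110, which rounds up to **445**. The noncentral t calculation also gives 445.
- One-sided 0.025: 2 × (1.960 + 0.842)² × 0.3988 / 0.01110, which rounds up to 564 (565 by noncentral t).

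For the total, 890 × 1.10 = 979, in line with the stated 980. The protocol's 445 therefore belongs to one-sided 0.05 and not to 0.025.

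**Step 2: power under each reading of the bound.** The standard error is SD × sqrt(2/n). At 445 per arm it is 0.6315 × sqrt(2/445) = 0.0423, so margin/SE = 2.489. By the normal approximation:

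- One-sided 0.05: Φ(2.489 − 1.645) = Φ(0.844) = 0.801
- One-sided 0.025: Φ(2.489 − 1.960) = Φ(0.529) = 0.702

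The noncentral t values are:

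| Evaluable per arm | One-sided 95% limit (0.05) | Two-sided 95% limit (0.025) |
|---|---|---|
| 441 (980 less 10%) | 79.7% | 69.7% |
| 445 | 80.0% | 70.1% |
| 490 (all 980) | 83.3% | 74.2% |

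The figures must be compared within a row. The difference is 9 to 10 percentage points in each.

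**Step 3: the borderline zone.** The smallest observed ratio that still passes is exp(−0.1054 + t × SE). At 445 per arm it is 0.9650 at one-sided 0.05 and 0.9780 at 0.025, so the largest passing shortfall is 3.5% or 2.2%. Only a result between these two values would be decided differently.

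**Step 4: set the two sections side by side.**

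| | Section 4.4 | Section 9.2 |
|---|---|---|
| Endpoint | Ventilator-free days at day 28 | Same |
| Null hypothesis | Restricted arm inferior by 10% | Same |
| Direction | One-sided | Only an upper bound is used |
| Level | 0.05 | 95% |

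Rejecting when a one-sided 95% upper limit is below the margin is the same act as rejecting a one-sided test at 0.05. That limit is also the upper limit of a two-sided 90% interval. Every row then agrees. The two-sided reading requires Section 9.2 to have halved the level set in Section 4.4 without saying so.

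**The case for a change.** The best case for a change is that the rule actually applied to the data is in Section 9.2, not Section 4.4. Section 9.2 does not refer back to the level in 4.4, and it uses a different method: a nonparametric interval for medians in place of a log-scale t-test. One could say that a reader may therefore not import one-sided 0.05. One could add that the protocol did not leave the rule to the analysis plan, since it gave a level, a bound and a threshold but stopped short of the side. The decision threshold for the primary endpoint of an open-label trial should not be open to choice once results are known.

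Part of this stands. The side is not written in Section 9.2, Section 9.1 does not supply it, and an unqualified 95% interval is often read as two-sided. The power figures are also correct for the Section 4.4 model.

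The rest does not carry. A change of method does not change the error level chosen for the same hypothesis and margin, and Section 4.4 is the only place that states side and level together. The general sentence in Section 9.1 applies where appropriate, and the superiority test in Section 9.2 is a separate, later step that can have its own interval. Because the method in Section 9.2 is itself left open, the analysis plan has to specify the interval in any case, and its side is an ordinary part of that. Finally, the 70% figure describes the t-test in 4.4. The power of the planned comparison of medians cannot be computed from the protocol, so the loss under the actual analysis is unknown.

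**Conclusion.** The concern does not call for a change. The side of the bound in Section 9.2 is unstated, but Section 4.4 fixes a one-sided 0.05 test for the same endpoint, null hypothesis and margin, and a single 95% upper limit is the matching decision rule. Read together, the sections agree and the 80% power at 445 per arm stands on the protocol's own model.

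If a two-sided 95% interval were nevertheless used, power on that model would be 70.1% instead of 80.0% at 445 per arm, or 74.2% instead of 83.3% at 490. Only an observed shortfall between about 2.2% and 3.5% (at 445 per arm) would be judged differently. These figures assume equal arms, a coefficient of variation of 0.70 and the log-scale t-test, and they do not transfer to the comparison of medians. The departure would be in the strict direction: nominally, neither reading exceeds a one-sided 5% error rate, although the actual level of the unnamed nonparametric method cannot be checked from the protocol.

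This is therefore a gap in wording that an analyst fills from Section 4.4 or the analysis plan. Writing in the word one-sided would be harmless, but it would alter no stated number and lead to no different sound conclusion.

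### Sections 4.4 and 9.2 describe different non-inferiority tests, and the 12-hour argument in 4.4 does not support the 10% margin on VFD-28

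*Protocol*

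**What the plan says.** Protocol 4.4 sizes the trial on a one-sided non-inferiority t-test "targeted at 0.05 significance level", with 445 patients per arm. The test is "for the difference in means of log–transformed normalized data has a 80% power" to reject inferiority of the restricted arm's VFD-28 to the liberal arm's "by a margin of 10% anticipating on a coefficient of a variation of 0.70". The next paragraph gives the clinical reading of the 10%: a more than 10% increase in the "duration of mechanical ventilation will reduce the VFD-28 with > 12 hours", a figure "calculated over the expected mean duration of mechanical ventilation of 5 days".

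Protocol 9.2 sets the decision. The rule begins "If the 95% CI upper bound for inferiority of the" restricted arm, and inferiority is rejected when that bound is below 10%. On the method it says: "We will use an appropriate nonparametric analysis method" to "evaluate the confidence interval for the difference between the two medians" of ventilator-free days in the two arms. It does not say whether the interval is one- or two-sided, or how a difference in days is set against a percentage.

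**The concern.** A stated power holds for one estimand, one margin and one alpha. Section 4.4 works with a ratio of means on the log scale. Section 9.2 works with a difference in medians in days, obtained nonparametrically. A power computed for the first cannot simply be quoted for the second. In addition, the log in 4.4 is undefined for a patient with VFD-28 = 0, a value the endpoint in 7.1.1 clearly allows.

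The second difficulty concerns the clinical case for the margin. A non-inferiority margin is a statement of how much loss is acceptable. Section 4.4 argues that half a day is the limit of what is acceptable, while the margin it adopts, 10% of VFD-28, concedes several times that. This rule decides the trial's primary conclusion, so a reader of the result needs to know what was conceded and with what power.

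**Working it through.** **Inputs from 4.4.** One-sided alpha 0.05; power 80%; margin 10%, i.e. ratio limit 0.90; coefficient of variation (CV) 0.70; 445 per arm; mean ventilation 5 days. From 8.2: hospital mortality 21%, used only to set a range.

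**1. Reproducing 445.**
- Log-scale SD = sqrt(ln(1 + 0.70²)) = sqrt(ln 1.49) = 0.631.
- Margin on the log scale = −ln 0.90 = 0.1054.
- n = 2 × (0.631 × (1.645 + 0.842) / 0.1054)² = 444.2, so 445 per arm.
- SE at 445 = 0.631 × sqrt(2/445) = 0.0423; power = Φ(0.1054/0.0423 − 1.645) = 80.1%.

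The match is exact. A margin of ln 1.1 would give 543, and a log SD of 0.70 would give 546. The 80% therefore belongs to a one-sided 5% test of log means with limit 0.90.

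**2. Sidedness of the 95% bound.**
- One-sided 95% bound: alpha 0.05, as in 4.4; power stays at 80%.
- Two-sided 95% interval (one-sided 0.025): power of 4.4's own test = Φ(0.1054/0.0423 − 1.960) = 70.2%; 80% would need 563.9, so 564 per arm.

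**3. Power of a medians rule at 445 per arm.** This depends on the distribution, which 4.4 does not give in a form usable for medians.
- If VFD-28 were lognormal, as 4.4 assumes, the SE of a sample median on the log scale is larger by sqrt(π/2). Power is then Φ(0.1054/0.0531 − 1.645) = 63%, or 51% with 1.960.
- VFD-28 is bounded at 0 and 28, so a more realistic model was simulated: deaths scored 0, lognormal ventilation time with mean 5 days, a bootstrap two-sided 95% interval for the difference in sample medians, and a margin of 10% of the control median. For ventilation-time CVs of 0.7, 1.0 and 1.5, equal arms pass in 95%, 88% and 82% of trials when deaths (about 29 to 31%) are set so that VFD-28 has CV 0.70. They pass in 99 to 100% at 21% deaths.

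On the realistic model the power is adequate, but it is not the 80% of 4.4.

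**4. What 10% means in days.**
- The justification: 10% × 5 days = 0.5 day = 12 hours. The base is ventilation time.
- Simple VFD-28 base without deaths: 28 − 5 = 23 days; 10% = 2.3 days = 55.2 hours; 55.2/12 = 4.6.
- Median base: in the model of step 3, the median VFD-28 is 28 minus the ventilation-time quantile at 0.5/(1 − deaths). For 21 to 30% deaths this is 22.1 to 24.0 days. Ten percent is 2.2 to 2.4 days, a factor of 4.4 to 4.8.
- Mean base: a variable confined to 0–28 with CV 0.70 has a mean of at most 28/1.49 = 18.8 days, so 10% is at most 1.9 days (factor 3.8). In the model of step 3 at CV 0.70 it is about 1.6 days (factor 3.2).

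It follows that 23 days and CV 0.70 cannot both be the mean and CV of VFD-28. On every base considered here the margin is well above 12 hours.

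**The case against.** The strongest reply is that little follows in practice. Sizing on a lognormal approximation and analysing nonparametrically is common, and a medians rule at 445 per arm has 82 to 100% power in the realistic model. The 95% bound may be one-sided, which agrees with 4.4. The base of the 10% can be inferred, since both sections define inferiority relative to the liberal arm. The interval method can properly be left to an analysis plan. All of this stands. What remains is that the protocol itself fixes two different estimands, attaches a power to only one of them, and argues for a margin with a figure from another scale.

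Three stronger readings are tempting and are not supported.
- **That 12 hours is the operative margin.** Every decision statement says 10%; the 12 hours is a faulty explanation of it.
- **That alpha is certainly inconsistent, or that the trial is underpowered.** The sidedness is ambiguous, and step 3 does not show a shortfall under the realistic distributions.
- **That the rule has an inflated error rate when deaths differ.** In simulation at CV 0.70, a 10% loss of mean VFD-28 caused by deaths passes the medians rule in 25%, 15% and 11% of trials. But that loss moves the median by only 5.0%, 6.1% and 6.6%, inside a 10% margin on medians. Passing is then a property of the chosen estimand and not a type I error. It is a reason to report more beside the median, not evidence that the rule fails on its own terms.

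**Conclusion.** The point holds as a contradiction within the protocol and needs correction, because it concerns the primary decision rule. The mismatch of scale and estimand between 4.4 and 9.2 stands on any reading of the 95% bound. The mismatch of alpha is conditional: none if the bound is one-sided, and 70% instead of 80% power for 4.4's own test if the interval is two-sided.

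The clinical argument in 4.4 covers 0.5 day, while the margin concedes about 2.2 to 2.4 days on medians or 1.6 to 1.9 days on a mean consistent with CV 0.70. The range rests on assumed mortality (21 to 31%), deaths scored 0 and lognormal ventilation time with the protocol's mean of 5 days. That the margin exceeds 12 hours needs only a VFD-28 above 5 days. Which loss is clinically acceptable is not judged here.

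**What to change.** State one estimand, one margin in that estimand's unit and one alpha, identically in 4.4 and 9.2. If medians are kept:
- give the margin as 10% of the liberal-arm median VFD-28, with its value in days under the planning assumptions;
- say whether the bound is one-sided 95% or from a two-sided 95% interval;
- replace the 80% of the log-mean t-test with the power of this rule, and state the distribution assumed, including patients at 0;
- delete or correct the 12-hour sentence and justify the margin in VFD-28 days;
- say explicitly in 7.1.1 that death by day 28 scores 0;
- report the difference in mean VFD-28 and mortality beside the primary result, since a difference in medians responds weakly to excess deaths.

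A ratio of arithmetic means with limit 0.90 is an option, not a requirement. At CV 0.70 its SE on the log scale is 0.70 × sqrt(2/445) = 0.0469, so 445 per arm gives Φ(0.1054/0.0469 − 1.645) = 73% power, or 61% with 1.960. Reaching 80% would need 546 or 693 per arm.

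The cost is rewording of 4.4, 7.1.1 and 9.2 and some analysis code, with no new data items. The drawback is that the stated power may become less favourable and the margin must be defended as about 2 days instead of 12 hours.

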7. METHODS

7.1 Study parameters/endpoints

7.1.1 Main study parameter

The primary endpoint is the number of ventilator-free days and alive at day 28, defined as the number of days from day 1 to day 28; the patient is alive and breathes without assistance of the mechanical ventilator, if the period of unassisted breathing lasted at least 24 consecutive hours.

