7.6 Follow up of subject withdrawn from the study

Patients withdrawn from the trial will not be subjected to follow up.

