For these reasons, we opt for using deferred consent, where informed consent from a legal representative must be obtained as soon as possible, but always within 48 hours after randomization. If informed consent is not obtained, or if a legal representative denies participation within the time window of 48 hours, the patient is excluded and data will no longer be used. Thenceforth the patient is ventilated according to the policy of the attending physician.

Textbox 3 - Ventilation has the potential to harm the lungs – even after a short period of ventilation

Ventilation can harm the lungs, even after a short period of ventilation. If a patient, in the proposed trial, is already ventilated for several hours, injurious effects of ventilation could already be in place, largely reducing validity of the trial outcomes. From experimental animal studies we know that mechanical ventilation can cause effects within hours of ventilation with a high PEEP level.⁵⁷ These findings are in line with results from clinical studies, showing ventilator-related effects after relative short periods of ventilation, e.g. after ventilation during general anesthesia for surgery.⁵⁸ A recent randomized controlled trial of patients undergoing cardiac surgery with hypoxemia, comparing a ventilation strategy including a PEEP level of 8 cm H₂O with a ventilation strategy with a PEEP level of 13 cm H₂O, showed an important effect of mechanical ventilation on the incidence of postoperative pulmonary complications.⁵⁹

Textbox 4 – Experiences with deferred consent in critically ill patients

Most critically ill patients who need ventilation cannot be approached for informed consent for a study at ICU admission. Indeed, those patients are usually in severe respiratory distress, sedated or in coma. A prospective observational study on study recruitment practices in critically ill patients performed by a respected and experienced research group in Canada showed that the time from recognizing study eligibility to obtaining informed consent by a legal representative was as high as 12 hours, even while time from recognition to the first contact with a legal representative was as short as 2 hours.⁵⁵

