10.2.3 No deferred consent in patients who die before obtaining informed consent

In case a patient dies before informed consent could be obtained from the legal representative, we propose to use the data and inform the legal representative about the research without obtaining informed consent. This is in line with the advice from Jansen and colleagues regarding ethical validity and practical feasibility of deferred proxy consent in emergency critical care research and in line with the advice of the Central Committee on Research Involving Humans (CCMO, the Dutch national Ethics Committee) in these circumstances in the early lactate-directed therapy in the ICU.^{56,61}

The CCMO judged that the situation when a patient dies before consent could be obtained is comparable with the situation in which the research project has already finished at the time deferred consent can be obtained. They concluded that the legal representative should be notified about the study, but that seeking consent was not useful anymore due to the lack of consequences. The representation of the patient by a legal representative ends when the patient dies. In the Dutch law, the consent of the patient or his/her relative primarily relates to the participation in the study and not to using the data collected in the study.⁵⁶

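### Protocol section 9.2 fixes Kaplan-Meier curves and a log-rank test for time to freedom from ventilation without dealing with death as a competing event; if deaths are censored, the curve overstates liberation by day 28

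*Protocol*

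**What the plan says.** Section 9.2 first sets out the non-inferiority comparison of ventilator-free days at day 28 (VFD-28). It then continues: "Additionally, time to freedom from mechanical ventilation is expressed with" Kaplan-Meier curves, and "Differences between both PEEP arms will be analyzed using the" log-rank test. Section 9.3 names Kaplan-Meier for other time-dependent data. No competing-risk method appears anywhere in the protocol, and no sentence says whether a patient who dies on the ventilator is censored at death, kept at risk to day 28, or counted as having a different event.

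Other sections bear on this:
- Section 7.1.1 credits a day to the primary endpoint only if "the patient is alive and breathes without assistance of the mechanical ventilator".
- Section 8.2 gives the only mortality rate: "the hospital mortality in ventilated ICU patients is 21" per cent.
- Section 4.4 gives the ventilation time, in a figure "calculated over the expected mean duration of mechanical ventilation of 5 days".
- Section 10.2.1 requires consent "but always within 48 hours after randomization". For patients who die before consent, section 10.2.3 says "we propose to use the data and inform the legal representative about the research". Deaths of that kind are early and stay in the data; how many to expect is not stated.
- Section 7.6: "Patients withdrawn from the trial will not be subjected to follow up".

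**The concern.** Kaplan-Meier and the log-rank test are built for one type of event. Censoring a patient at death treats that patient as someone who could still have been weaned later, at the same rate as those left on the ventilator. The complement of the curve then answers a hypothetical question, namely what share would be liberated if nobody died. It is not the share of patients who come off the ventilator.

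A reader would naturally set this curve beside VFD-28, which gives no credit for days after death. With deaths censored, the two treat death in opposite ways. The log-rank test with deaths censored compares the rate of liberation among patients still alive and ventilated, not the probability of being liberated. At stake is how a supporting display and its p-value are read in a trial that aims to show that restricted PEEP is not worse.

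**Working it through.** **The plan's own figures.** The protocol gives no figure for this analysis. Its 445 per arm belongs to VFD-28 and reproduces: margin −ln(0.90) = 0.1054, log-scale SD √ln(1 + 0.70²) = 0.6315, and 2 × (1.645 + 0.842)² × 0.6315² / 0.1054² ≈ 444.2, so 445. Nothing below changes it.

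**Inputs.** Mean ventilation time 5 days (section 4.4); follow-up to day 28 (section 7.4); hospital mortality 21% (section 8.2). The 21% includes deaths after liberation, so it is a ceiling for the share *q* dying before liberation. The values of *q* below 21%, all death times and the spread of ventilation times are assumptions.

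**Step 1: closed form.** Take constant hazards with mean 5 days to liberation or death, so the total hazard is 0.2 per day, the liberation hazard λ = 0.2(1 − q) and the death hazard 0.2q.
- Proportion liberated by day 28: (1 − q)(1 − e^(−0.2×28)).
- 1 minus Kaplan-Meier, deaths censored: 1 − e^(−28λ).

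For q = 0.21, λ = 0.158. The first is 0.79 × (1 − e^(−5.6)) = 0.787. The second is 1 − e^(−4.424) = 0.988. The gap is 20.1 points. For q = 5%, 10% and 15% the gaps are 4.9, 9.7 and 14.5 points.

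**Step 2: vary when patients die.** Simulation with lognormal ventilation time (mean 5 days, coefficient of variation 0.7, assumed), a fixed share q dying before liberation, and 400,000 patients per cell. Overstatement at day 28 in percentage points, deaths censored:

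| Timing of deaths | q = 5% | 10% | 17% | 21% |
|---|---|---|---|---|
| Uniform, days 5–28 | 2.6 | 3.8 | 4.9 | 5.0 |
| Uniform, days 0–28 | 3.1 | 5.0 | 7.0 | 7.6 |
| Exponential, mean 10 days | 4.1 | 7.4 | 11.2 | 13.0 |
| Exponential, mean 6 days | 4.8 | 9.3 | 15.5 | 18.6 |
| Exponential, mean 3 days | 5.0 | 10.0 | 16.8 | 20.9 |

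A repeat run gave 2.5 for the smallest cell. At q = 21% the true proportion liberated is about 0.79 in every row, while 1 minus Kaplan-Meier runs from 0.840 to 0.998. With a coefficient of variation of 1.0 or 1.5, the days 5–28 gap at 21% becomes 6.9 or 7.1 points, and the mean 6 days gap 18.7 or 17.8.

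**Step 3: the other handling.** If patients who die stay in the risk set to day 28 and nobody is otherwise lost, the Kaplan-Meier product telescopes and its complement is simply the number liberated divided by the number randomised. The overstatement is zero.

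**Step 4: what the log-rank compares.** Keep the liberation hazard at 0.158 in both arms and let the death hazard be 0.042 in one and 0.063 in the other (the second value is purely illustrative). The proportions liberated are 78.7% and (0.158/0.221)(1 − e^(−0.221×28)) = 71.3%. The complement of Kaplan-Meier with deaths censored is 98.8% in both. The censored log-rank correctly finds equal hazards here, and the 7.4-point difference in liberation is not what it tests. In a different model, where a fixed group is destined to die without being liberated, more deaths also change the liberation hazard and the test registers part of the difference.

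**The case against.** The strongest reply is that section 9.2 states nothing false. It names two methods and sets no rule for deaths; under one ordinary rule, keeping the dead at risk to day 28, those methods give the right proportion. Such a rule could sit in a statistical analysis plan, which was not available. The analysis is also only additional. ICU, hospital and 90-day mortality are separate endpoints in section 7.1.2 and ICU mortality is reported for safety under section 8.2, so a difference in deaths would not go unseen.

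Much of this stands. The protocol cannot be said to censor deaths, and the size of the problem rests on assumptions. What does not follow is that nothing needs changing. Section 9.2 fixes the estimator and the test, and a censoring rule written elsewhere would not change the estimator it names. Because withdrawn patients are not followed, an estimator that handles both censoring and a competing event is also the cleaner choice.

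The log-rank part of the concern is limited as well. With deaths censored it is a valid test of the cause-specific liberation hazard, which is a legitimate question about weaning. A reader might infer that the test loses a calculable amount of power, or that it loses almost nothing when deaths are late. Neither is supported: as step 4 shows, how far the test reflects a difference in deaths on the ventilator depends on the model assumed, not on timing alone. No power figures are claimed.

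**Conclusion.** The point holds as a cheap improvement to a supporting analysis. Section 9.2 fixes single-event methods for an outcome that death precludes. If deaths are censored, the curve overstates liberation at day 28 by about 2.5 to 21 points over the assumed range of 5% to 21% dying before liberation, more when deaths are earlier; if the dead are kept at risk, by nothing. The upper end takes all hospital mortality as early deaths on the ventilator, so it is a ceiling and not an expected value.

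A reader might go further and infer that the primary result is biased. The documents do not support that: VFD-28 already requires the patient to be alive. The non-inferiority decision, the sample size and the mortality comparisons do not use this curve.

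**What to change.** In section 9.2, replace the Kaplan-Meier display with the Aalen-Johansen cumulative incidence of liberation to day 28, with death as a competing event, and show the cumulative incidence of death before liberation beside it. Censor only withdrawn patients. Compare the arms with Gray's test or a subdistribution hazard ratio with its 95% confidence interval. The log-rank test may stay if it is labelled as a test of the cause-specific liberation hazard. Kaplan-Meier remains suitable for mortality under section 9.3.

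The cost is two or three sentences and standard R code. Section 7.4 already collects time of extubation and daily life status to day 28, so no new data are needed. The drawback is that a subdistribution hazard ratio mixes effects on weaning and on death, which is why the death curve should be shown with it.
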